The patients were divided into three subgroups for data analysis. Group 1 included patients with history-indicated cerclage, who had second-trimester pregnancy loss associated with painless cervical dilatation in the absence of labor or placental abruption, or previous cerclage due to painless cervical dilatation in the second trimester. Group 2 comprised patients with ultrasound-indicated cerclage, who had a history of spontaneous preterm birth before the 34th week previously and their cervical length was <25 mm before the 24th week of gestation in the current singleton pregnancy, or who had <10 mm cervical length in the current singleton pregnancy without history. Group 3 consisted of patients undergoing rescue cerclage, who had premature cervical dilatation and exposure of fetal membranes in the vagina, was detected in ultrasound or speculum examination of the cervix. All cervical cerclage procedures were performed by a senior obstetrician using the McDonald technique with Mersilene tape or No:1 proline. We collected the following data from medical records: maternal age at cervical cerclage, gravidity, parity, body mass index, history of a cervical cone biopsy, history of premature birth and cervical cerclage, procalcitonin level, C-reactive protein (CRP) level, gestational age at cerclage, pre-and post-cerclage cervical length (CL), week of birth, pregnancy complications (preterm premature rupture of the membranes (PPROM), abruptio placenta, chorioamnionitis). We defined successful cerclage as postponing birth until after the 28th week of gestation and a 'good outcome' was defined as delivery beyond 34 completed weeks. We reviewed the indications and the pregnancy outcomes (miscarriage, gestational age at delivery, birth weight, prolongation of pregnancy, and rate of preterm birth before 34 weeks) of cervical cerclage and analyzed the factors associated with successful cervical cerclage in our perinatal medical center.

Moreover, receiver operating characteristic (ROC) curves were used to calculate the pre-cerclage and post-cerclage CL cut-off value required to predict if birth could be postponed birth until after the 28th week of gestation in women with cervical insufficiency (CI). Thus, we

extracted significant factors for a successful cervical cerclage for long-term pregnancy sustenance in women with CI.

Statistical Analysis Plan

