All data were analyzed using the statistical software package SAS version 15.2 (SAS Institute Inc.). The Kolmogorov-Smirnov test was used to test the normality assumption. The three groups of patients were compared in terms of three outcomes, successful cerclage, good outcomes, and PPROM. For categorical variables, a comparison among the three groups of patients regarding socio-demographics and clinical features was conducted using the Chi-square or Fisher's exact test, as appropriate. For continuous variables, the three groups of patients were compared using the Kruskal-Wallis test or analysis of variance (ANOVA), as appropriate. Within each group, we compared the patients in terms of successful cerclage, good outcomes, and PPROM. A p-value less than 0.05 was considered statistically significant. The predictive power of pre- and post-operation cervix length in identifying successful cerclage was evaluated using receiver operating characteristic (ROC) curves, and the area under the curve (AUC) determined the discriminative ability of the parameters. The optimal cut-off values are derived using Youden's Index.

Results

We included 129 patients with a singleton pregnancies in this study. Three membrane rupture complications occurred during the cervical cerclage procedure (all three cases were in the emergency cerclage group and the pouches were prolapsed). Externally, no uncontrollable bleeding or injury to the bladder and/or rectum occurred during cerclage. The sample size was 129 patients, with 32 in the history-indicated cerclage group (G1), 62 in the ultrasound-indicated cerclage group (G2), and 35 in rescue cerclage group (G3). Only six (4.6%) pregnancies resulted in miscarriage before 20 weeks of gestation. Among these three groups, significant differences were observed in gravidity, parity, history of preterm birth, and history of CI. In group 1, the average gravidity was 4.69 (2.05), whereas in groups 2 and 3, it was much lower at 2.47 (1.83) and 2.23 (3.81), respectively. Similarly, parity was much higher in group 1 than in groups 2 and 3.

We compared the three groups in terms of factors that could affect cervical cerclage success and pregnancy outcomes of cerclage cases. Among these three groups, significant

differences were observed in cerclage week, the time elapsed from cerclage to childbirth, post-operation cervix length, complication rates, successful cerclage and good outcomes (delivery beyond 34 completed weeks).

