The average cerclage week was 14.39 (1.99) in group 1, but the week of cerclage performance was later in groups 2 and 3 (21.47 (2.97) and 20.98 (4.14), respectively).

The average time elapsed from cerclage to childbirth was much longer in group 1, with an average of 143.63 (41.27) days, whereas it was relatively shorter in group 2, with an average of 94.46 (35.16) days. The shortest time elapsed from cerclage to birth was observed in group 3, with an average of 69.82 (49.35) days.

In groups 1 and 2, the percentage of patients with successful cerclage was much higher (90.6% and 88.7%, respectively) than in group 3 (66.7%). Similarly the percentage of patients with good outcomes was much higher for the patients in groups 1 and 2 in comparison with group 3. The earlier cerclage is applied after CI is identified, the longer the time from cerclage to birth.

We also evaluated the effects of preop cervical length, postop cervical length, preop procalcitonin value, preop CRP, cerclage week, and cerclage material on cerclage results for each group separately. Within group 1, we compared the patients who had successful cerclage with the patients who did not in terms of pre-op cx, post-op cx, procalcitonin, CRP, the week of cerclage, and the material of cerclage. We found significant difference in these two groups in terms of the average procalcitonin; however, we only had three patients with unsuccessful cerclage and all three patients had the same procalcitonin values. Therefore, we did not report the p-value for this comparison. Based on this result, although we cannot clearly say that high procalcitonin values reduce cerclage success in the prophylactic cerclage group, the effects of procalcitonin need to be studied on cerclage success in more detail.

In the prophylactic cerclage group, there was also a significant difference between patients with and without PPROM ($p<.0001$). The average post-operation cervix length for patients without PPROM was 34.5 (4.64) mm, whereas the average post-operation cervix length for patients with PPROM was 19.4 (0.85) mm. We concluded that the longer the postoperative cervix length, the lower the probability of PPROM in the prophylactic cerclage group.

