As a result of our analysis for group 3, we found no significant differences (All p -values $>.05$). Lastly, we used ROC curves to calculate the pre-cerclage and post-cerclage CL cut-off value required to predict if birth could be postponed until after the 28th week of gestation in women with CI. Thus, we extracted significant factors for a successful cervical cerclage for long-term pregnancy sustenance in women with CI. In group 2, we used Youden's Index to determine an optimal cut-off value for the post-operation cervix length and the pre-operation cervix length. For the post-operation cervix length, the optimal cut-off value was determined as 23.87 with sensitivity=0.83, specificity=0.72 (AUC=0.78). The area under curve

(AUC) for the analysis with the pre-operation cervix length was equal to 0.52, meaning that this parameter did not have a predictive power for identifying successful cerclage.

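### The cervical-length ROC analysis is planned for women with CI without a group limit but reported for group 2 only, with no reason given

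*Combined protocol and SAP*

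**What the plan says.** The Study Protocol says that ROC curves will give the pre- and post-cerclage length cut-off needed to "predict if birth could be postponed birth until after the 28th week of gestation in women with cervical insufficiency (CI". No cerclage group is named.

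The Statistical Analysis Plan repeats the analysis: "The predictive power of pre- and post-operation cervix length in identifying successful cerclage was evaluated using receiver operating characteristic (ROC) curves". On the threshold it adds "The optimal cut-off values are derived using Youden's Index". It names no group and does not say whether the curves are pooled or drawn per group.

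The Results first restate the purpose in general terms: "Thus, we extracted significant factors for a successful cervical cerclage for long-term pregnancy sustenance in women with CI". They then give figures for one group: "In group 2, we used Youden's Index to determine an optimal cut-off value for the post-operation cervix length and the pre-operation cervix length". For post-operation length these are a cut-off of 23.87, sensitivity 0.83, specificity 0.72 and AUC 0.78. For pre-operation length only an AUC of 0.52 is given, without a cut-off.

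The within-group comparisons come just before. In group 2, post-operation length differed by successful cerclage (p=.015). In group 1, the reported difference in that length was by PPROM, not by success. For group 3 the Results say "As a result of our analysis for group 3, we found no significant differences (All p -values $>.05".

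**The concern.** An analysis described without a group restriction appears for one group out of three. That group is the only one in which the preceding test of the same variable against the same outcome was reported as significant. The other two groups and the whole cohort have no AUC, so a reader cannot tell whether post-operation length separates success from failure generally, or only where it had already been seen to do so.

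If results are shown only where an earlier test was positive, the reported AUC and cut-off tend to look better than the full evidence. The wording adds to this. The sentences that introduce the ROC refer to women with CI in general and to sustaining pregnancy over the long term. The figures that follow concern ultrasound-indicated cerclage and birth after week 28. The protocol has a separate and later endpoint, delivery beyond 34 completed weeks, which this ROC does not address.

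**Working it through.** **1. Plan against report**

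| Item | Study Protocol and SAP | Results |
|---|---|---|
| Population | Women with CI, no group named | Group 2 |
| Post-operation length | ROC and Youden cut-off | AUC 0.78, cut-off 23.87 |
| Pre-operation length | ROC and Youden cut-off | AUC 0.52, no cut-off |
| Groups 1 and 3, cohort | Not excluded | Nothing reported, no reason |

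**2. What can be reproduced.** The cut-off and AUC need patient-level data, so only consistency checks are possible. Inputs are the group 2 post-operation lengths in the Results: 26.1 (7.37) mm with success and 18.0 (9.23) mm without.

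- Normal-theory AUC = Φ(8.1/√(7.37² + 9.23²)) = Φ(0.686) = 0.75, near the stated 0.78.
- Pooled t-test (the two-group test is not named, so this is an assumption): with 55 successes and 7 failures, t = 8.1/3.04 = 2.66 and p=.0099. With 55 and 6, t = 8.1/3.24 = 2.50 and p=.0153, close to the stated .015.
- Sensitivity and specificity: with 7 failures, 5/7 = 0.71 and 6/7 = 0.86, so neither 0.83 nor 0.72 can come from the failures. With 6 failures, 5/6 = 0.83 and, for example, 39/54 = 0.72 fit, if failure is the positive class.

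The group 2 ROC may therefore rest on 6 failures, with at least one length missing. That is an inference from rounding.

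**3. Where the failures are.** Group sizes are given as "with 32 in the history-indicated cerclage group (G1), 62 in the ultrasound-indicated cerclage group (G2), and 35 in rescue cerclage group (G3" and success rates as "90.6% and 88.7%, respectively) than in group 3 (66.7" (per cent).

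- Group 1: 29/32 = 90.6%, so 3 failures, as the Results state.
- Group 2: 55/62 = 88.7%, so 7 failures.
- Group 3: 23/35 = 65.7% and 24/35 = 68.6%, so no count out of 35 gives 66.7%. 22/33 does, which means 11 failures if two outcomes are unknown (assumption). Taking 35 at face value, 0.333 × 35 = 11.7, or about 12.
- Total: 3 + 7 + 11 = 21, or 3 + 7 + 12 = 22.
- Share in group 2: 7/21 = 33% or 7/22 = 32%. Outside it: 14/21 = 67% or 15/22 = 68%. If the ROC used only 6 failures, it covers 6/21 = 29% or 6/22 = 27%.
- Group 2 is 62/129 = 48% of the women.

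**4. Could group 3 have supported an AUC?** The Hanley–McNeil variance is [A(1−A) + (m−1)(Q1−A²) + (n−1)(Q2−A²)]/(mn), with m women in the positive class and n in the other, Q1 = A/(2−A) and Q2 = 2A²/(1+A). At A = 0.78, Q1−A² = 0.0309, Q2−A² = 0.0752 and A(1−A) = 0.1716. The result depends on which class is called positive, so both are shown.

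- Group 2, 55 and 7. Success positive: √(2.294/385) = 0.077. Failure positive: √(4.418/385) = 0.107.
- Group 3, 22 and 11, at the same AUC purely for comparison. Success positive: √(1.573/242) = 0.081. Failure positive: √(2.060/242) = 0.092.

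The precision is about the same in the two groups, so the number of failures does not explain leaving out group 3.

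**5. Precision of the reported AUC.** 0.78 ± 1.96 × SE gives 0.63–0.93 (success positive) or 0.57–0.99 (failure positive) with 55 and 7. With 54 and 6 the SEs are 0.082 and 0.115, giving 0.62–0.94 or 0.55–1.00 (capped at 1). The Results give no interval.

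**The case against.** The best defence is that the Results are properly labelled. The cut-off is introduced as a group 2 result, and no later sentence extends it. The general sentences stand before any ROC figure, nearly repeat the protocol's statement of purpose and carry no number. A reader might infer that 23.87 is claimed for all women with CI, but the documents do not say so. What remains is that the framing is wider than the result and should be narrowed. The reference to long-term sustenance is softened by the sentence before it, which names week 28, but the phrase still reaches past that endpoint.

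A reader might also infer that group 2 was chosen because its test was significant. The documents give no reason, so this cannot be asserted. Within group 2 the unfavourable pre-operation AUC of 0.52 was reported, so there is no sign of selection between the two lengths. Three failures are a fair reason not to derive a cut-off in group 1. None of this accounts for group 3, which has the most failures. Lengths might be harder to obtain in rescue cerclage, but the Results say that both lengths were examined against outcome in each group, so some data existed. How many are missing is not stated.

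A comparison of average lengths between groups should not be pressed. The 34.5 mm (group 1) and 26.3 mm (group 2) figures describe women without PPROM, a subset chosen on a different outcome.

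**Conclusion.** The point holds as one of incomplete reporting with a risk of selection. The ROC analysis is planned without a group limit and reported for one group of three, the only one with a reported difference in the same variable by the same outcome. No reason is given, and about two-thirds of the failures (14 of 21, or 15 of 22) lie outside it. The direction of any effect on the AUC cannot be worked out without the missing results.

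The verdict assumes that the women with CI in the plan are the cerclage cohort of 129, which the text implies but does not define. It also rests on about 11 failures in group 3 (22/33) or about 12 (n=35); the choice does not change the conclusion. It does not rest on any claim about why group 2 was chosen, nor on the cut-off having been applied to other groups.

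**What to change.** - Report pre- and post-operation AUCs with confidence intervals, and the numbers of successes and failures used, for each group. Keep group 1 descriptive, without a cut-off, because it has 3 failures.
- Add a group-stratified AUC over all women with known length and outcome, comparing successes with failures within the same group. State how many women are missing a length or an outcome, which would also settle the 66.7% in group 3.
- State why a cut-off was derived in group 2, and whether this was decided before the within-group tests were seen.
- Label 23.87 as an exploratory cut-off for birth after week 28 in ultrasound-indicated cerclage only, and limit any cut-off conclusion to that group and endpoint. The general sentences can still describe the aim of the ROC work once all groups are reported.

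The cost is a few extra analyses on data already collected and a narrower conclusion.

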Within group 2, there were significant differences between patients with and without successful cerclage in terms of post-cerclage cervical length and procalcitonin levels. The average post-op cervix length was 26.1 (7.37) mm for the patients with successful cerclage, whereas the average post-op cervix length was 18.0 (9.23) mm for patients without successful cerclage ($p=.015$). The average procalcitonin level was 0.06 (0.03) $\mu\text{g/L}$ for patients without successful cerclage, and was 0.04 (0.02) $\mu\text{g/L}$ for patients with successful cerclage.

In the ultrasound-indicated cerclage group, the mean postoperative cervix length of patients with successful cerclage was longer. In this group, we can say that as the postoperative cervical length increases, the success of the procedure increases.

When we compared the patients with and without PPROM in group 2, we found that there was a significant difference between the groups in terms of post-op cervix length ($p=.010$). Patients with PPROM had a shorter post-op cervix length (18.6 (9.02) mm) than patients without PPROM (26.3 (7.32) mm). We conclude that in the ultrasound-indicated cerclage group, as in the prophylactic cerclage group, the longer the postoperative cervix length, the lower the likelihood of PPROM. In this group, similar to the findings for successful cerclage, there were also significant differences between patients with and without good outcomes in terms of post-op cervix length and procalcitonin levels. The average length of post-op cervix length was 27.4 (6.56) mm for patients with good outcomes, whereas the average post-op cervix length of was 19.6 (8.60) mm for patients poor outcomes ($p<.001$). The average procalcitonin level was 0.05 (0.02) $\mu\text{g/L}$ for patients with poor outcomes, and was 0.04 (0.02) $\mu\text{g/L}$ for patients with good outcomes.

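### Group 2 cut-off of 23.87: sensitivity 0.83 and specificity 0.72 cannot both be correct with success as the positive class; state the event coded and the 2×2 counts

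*Combined protocol and SAP*

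**What the plan says.** The Study Protocol section sets the purpose of the ROC analysis: a cervical-length cut-off that predicts whether birth is deferred past 28 weeks. That is the same threshold that defines success. The Statistical Analysis Plan section states: "The predictive power of pre- and post-operation cervix length in identifying successful cerclage was evaluated using receiver operating characteristic (ROC) curves". It takes cut-offs from Youden's Index.

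The Results section gives these figures for group 2:

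- Size: "62 in the ultrasound-indicated cerclage group (G2").
- Success in groups 1 and 2: "the percentage of patients with successful cerclage was much higher (90.6% and 88.7%, respectively"), so 88.7% in group 2.
- Post-operative length in the successes: "The average post-op cervix length was 26.1 (7.37) mm for the patients with successful cerclage". For the failures the mean is 18.0 mm (SD 9.23), and the comparison carries p=.015.
- Accuracy at the post-operative cut-off: "the optimal cut-off value was determined as 23.87 with sensitivity=0.83, specificity=0.72 (AUC=0.78").
- Pre-operative length: AUC 0.52, "meaning that this parameter did not have a predictive power for identifying successful cerclage".

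For the cut-off, the text gives no 2×2 counts, no number of women analysed, no explicit positive class, no direction of the test and no confidence interval.

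**The concern.** With success as the positive class, sensitivity is the share of successes above the cut-off and specificity is the share of failures below it. Group 2 has very few failures, so specificity can take only a handful of values, and 0.72 is not one of them.

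This is the only cut-off that the study reports, and obtaining one is a stated aim. Someone using it needs to know which figure describes the women who delivered early and which describes those who did not. The two groups differ roughly eightfold in size (55 against 7), so exchanging the labels changes how many women with a good course fall below the cut-off. The figure that describes the failures rests on 6 or 7 women, whichever figure it is.

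**Working it through.** **Inputs.** Group 2 size 62, success 88.7%, sensitivity 0.83, specificity 0.72, and the post-operative means and SDs, all from Results. The event is success at 28 weeks, from the Statistical Analysis Plan and Study Protocol sections.

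**Step 1: number of failures.** Among all fractions k/n with n up to 62, only 55/62 and 47/53 round to 88.7%. So there are 62 − 55 = 7 failures, or 53 − 47 = 6. Missing cervical lengths can only lower the number of failures in the ROC analysis.

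**Step 2: attempt to reproduce the pair as worded (success positive).**

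- Specificity = failures below the cut-off / failures measured. With 7: 5/7 = 0.71, 6/7 = 0.86. With 6: 4/6 = 0.67, 5/6 = 0.83. The smallest denominator that rounds to 0.72 is 18 (13/18). The stated 0.72 is not attainable.
- Sensitivity = successes above the cut-off / successes measured. With all 55: 45/55 = 0.82, 46/55 = 0.84. The stated 0.83 is not attainable unless some successes are missing, for example 45/54 = 0.83.
- Over 1 to 7 failures and 40 to 55 successes, no split gives 0.83 and 0.72 together.

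**Step 3: failure as the event (length below the cut-off positive).**

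- Sensitivity = failures below / failures measured. Among denominators of 7 or fewer, only 5/6 rounds to 0.83.
- Specificity = successes above / successes measured. On all 55 women, 39/55 = 0.71 and 40/55 = 0.73, so 0.72 again fails. With fewer it works: 39/54, 38/53 and 34/47 all round to 0.72 (as do 36/50, 33/46 and 31/43).
- Each fit implies a reduced number. 39/54 with 5/6 uses 60 of 62 women, 38/53 uses 59, and 34/47 uses 53. None of these is disclosed.

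So on the full 62 women neither labelling produces either figure.

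**Step 4: side checks, supportive only.**

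- A pooled two-sample t-test on 26.1 (7.37) against 18.0 (9.23) gives p=.0155 for 54 against 6 and p=.0099 for 55 against 7. Over rounding of the inputs the ranges are .0143–.0168 and .0090–.0108. The reported .015 agrees with 6 measured failures. For 47 against 6 the range is .0157–.0184, which does not include .015. The SAP names no two-group test, so little weight can be put on this.
- Assuming normal lengths at 23.87, 1 − Φ((23.87 − 26.1)/7.37) = 62% of successes lie above and Φ((23.87 − 18.0)/9.23) = 74% of failures lie below. A success figure of 72% is closer to 62% than 83% is.
- Group 3's success rate of 66.7% is not attainable on its 35 women (23/35 = 65.7%, 24/35 = 68.6%) but fits 22/33, so undisclosed reduced denominators are plausible elsewhere in the data.

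**Step 5: effect of a label swap, failures held fixed.** Using the nearest whole counts and 54 successes, the share failing below the cut-off = failures below / (failures below + successes below). Successes below are 54 − 45 = 9 as worded and 54 − 39 = 15 if swapped.

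| Failures | As worded | Swapped | Fall |
|---|---|---|---|
| 7 | 5/(5+9) = 36% | 6/(6+15) = 29% | about 7 points |
| 6 | 4/(4+9) = 31% | 5/(5+15) = 25% | about 6 points |

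The Youden index is 0.83 + 0.72 − 1 = 0.55 under either labelling.

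**Step 6: precision.** Exact (Clopper-Pearson) 95% intervals for the failure-side figure are 0.36–1.00 for 5/6 and 0.29–0.96 for 5/7.

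**The case against.** The strongest reply is that no calculation error has been shown. The text never names the positive class for this pair. Its statement about identifying success in Results is attached to the pre-operative AUC, which is the same under either labelling. If failure was the event, both printed figures are right, and what is missing is a label and a number analysed. If instead 5/7 = 0.714 was printed as 0.72, the slip is 0.006, and 45/54 = 0.83 then fits the wording with one length missing. The main group 2 conclusion, that longer post-operative length goes with success, rests on the means and p-value and does not move.

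Most of this stands as a limit on cause and size. It does not remove the point. The SAP names success as the target, a reader will take sensitivity and specificity accordingly, and on that reading the pair cannot be obtained. Every empirical 28-week reading that comes close also needs women to be missing without disclosure.

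Three stronger readings are tempting and not supported:

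- **That a swap of labels is proven.** It is the only 28-week empirical reading that reproduces both figures, but a rounding slip or a smoothed curve cannot be excluded.
- **That the share failing below the cut-off falls from 36% to 25%.** This contrast takes 5/14 from 7 failures and 5/20 from 6 failures, so it mixes a change of label with a change in the number of failures.
- **That the ROC was run on the 34-week outcome**, since 13/18 = 0.72 and 35/42 = 0.83. This contradicts the stated 28-week endpoint. If the same women entered both comparisons, the reported SDs also narrowly exclude that split.

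**Conclusion.** The reported pair is wrong as worded. Specificity for success cannot be 0.72 with 6 or 7 failures, whatever lengths are missing. This rests on three things: success at 28 weeks being the positive class, as the SAP indicates; an empirical ROC curve; and the stated 88.7% being a fraction of at most 62 women. Confidence is high on that incompatibility and does not extend to its cause.

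The consequence is moderate. The value 23.87, the AUC of 0.78 and the conclusion on pre-operative length are unaffected by relabelling. If the classes were exchanged, sensitivity and specificity for success become 0.72 and 0.83, with the 6-to-7-point change shown above. The wide intervals matter at least as much, because the figure that describes the failures probably rests on 5 of 6 or 5 of 7 women. This should be fixed, but it does not overturn the study's findings.

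**What to change.** Re-run the group 2 ROC on the 28-week endpoint and report:

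1. the event coded and the direction of the test;
2. the number of successes and failures with a measured post-operative length, with reasons for any of the 62 women not included;
3. the 2×2 counts at 23.87.

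If failure was the event, say so beside the figures, or exchange them and keep success as positive. If success was the event, correct the figures to match the counts. If a smoothed curve was used, name the method.

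Give exact confidence intervals with the final values, and note that the cut-off was both chosen and evaluated on the same 6 or 7 failures.

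The cost is one re-run on existing data and a few lines of text. The reported accuracy will look less precise than it does now.

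### Group 2 was selected on pre-operation cervical length with a history-dependent ceiling, so its single pooled AUC of 0.52 cannot support the conclusion that this length does not predict success.

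*Combined protocol and SAP*

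**What the plan says.** The Study Protocol defines the ultrasound-indicated group by two routes. Women with an earlier spontaneous preterm birth before 34 weeks qualify if "their cervical length was <25 mm before the 24th week of gestation in the current singleton pregnancy". The alternative route takes women "who had <10 mm cervical length in the current singleton pregnancy without history". The outcome is set in the same section: "We defined successful cerclage as postponing birth until after the 28th week of gestation".

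The Statistical Analysis Plan evaluates pre- and post-operation length by ROC curve, AUC and Youden's Index. It does not mention the entry routes, adjustment for history, or confidence intervals. The Results give ROC figures for group 2 only: AUC 0.78 for post-operation length, and for pre-operation length "AUC) for the analysis with the pre-operation cervix length was equal to 0.52, meaning that this parameter did not have a predictive power". No interval, no count by route and no summary of pre-operation length in group 2 is given. The aim is stated as prediction in women with cervical insufficiency, which is wider than women already selected on length.

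**The concern.** The variable under test is also the entry variable, and its ceiling depends on history. By definition every group 2 woman between 10 and 25 mm has the qualifying history, and every woman without it is below 10 mm. Two things follow.

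- **Range restriction.** Lengths of 25 mm and above are absent. Restricting the range of a predictor generally lowers its AUC relative to an unrestricted population.
- **Pooling two ceilings.** A pooled AUC counts success–failure pairs that straddle the routes. In those pairs a difference in length is mixed with a difference in history, so any effect of history at equal length enters the AUC as if it were an effect of length.

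At stake is a plain negative statement about a routine measurement, set beside a positive one for post-operation length. A reader could discard pre-operation length on evidence that cannot bear that conclusion.

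**Working it through.** **Inputs from the documents.** Group 2 size: "62 in the ultrasound-indicated cerclage group (G2", that is 62. Success 88.7%: 55/62 = 0.887, so 55 successes and 7 failures. Pre-operation AUC 0.52. Ceilings 25 mm and 10 mm.

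**Can 0.52 be reproduced?** No. That would need the group 2 distribution of pre-operation length by outcome, which is not reported. The post-operation AUC can be checked approximately from the reported means and SDs with a binormal model: Φ((26.1 − 18.0)/√(7.37² + 9.23²)) = Φ(8.1/11.81) = Φ(0.686) = 0.754. That is reasonably close to the stated 0.78.

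**Precision of 0.52 (Hanley–McNeil).** With A = 0.52:
- Q₁ = A/(2 − A) = 0.3514; Q₂ = 2A²/(1 + A) = 0.3558; A² = 0.2704.
- Variance = [A(1 − A) + 54(Q₁ − A²) + 6(Q₂ − A²)]/(55 × 7) = [0.2496 + 4.3714 + 0.5123]/385 = 0.01333.
- SE = 0.115; 95% CI = 0.52 ± 1.96 × 0.115, about 0.29 to 0.75.

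The count of 7 may not be exact for the ROC. The post-operation sensitivity of 0.83 and specificity of 0.72 fit no fraction with denominator 7 or 55, but do fit 5/6 and 39/54. With 6 failures the interval is 0.28–0.76.

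**Effect of pooling (illustration; inputs assumed).** Length uniform on 5–25 mm with history and 2–10 mm without; odds of failure falling 7–10% per mm; overall failure 7/62; 30% or 50% of women in the no-history route. AUC is the probability that a success has the longer cervix. Within the history route it is 0.62–0.67, and within the no-history route 0.55–0.57. The pooled value depends on the assumed effect of history at equal length:

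| Odds ratio of failure, history vs none | Pooled AUC |
|---|---|
| 1/3 | 0.69–0.75 |
| 1 | 0.61–0.67 |
| 2 | 0.55–0.62 |
| 3 | 0.51–0.59 |
| 5 | 0.47–0.56 |

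With the same length effect throughout, pooling can erase it, leave it or exaggerate it. Counting only same-route pairs gives 0.59–0.66 at odds ratios 3–5, against 0.47–0.59 pooled.

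**Effect of truncation (second illustration; inputs assumed).** Length normal with mean 20, 25 or 30 mm and SD 8 before selection; history share 30–90%. An AUC of 0.70 without any entry rule becomes 0.61–0.66 within the 25 mm route and 0.55–0.57 within the 10 mm route. Pooled, it is 0.63–0.68 with no history effect, 0.55–0.63 at odds ratio 3 and 0.67–0.78 at 1/3. The entry rule with no history effect did not bring 0.70 down to 0.52.

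**The case against.** The strongest reply has four parts.

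1. A reader might infer that the entry rule itself pushed the AUC to 0.52, or that history cancelled a real length effect. The documents do not support that. The fall in the illustration needs history to raise risk at equal length; the protocol fixes who enters, not who is at higher risk. If history lowers risk, pooling inflates the AUC. This part of the reply stands in full.
2. Chance explains 0.52 as readily. With no history effect and a true pooled AUC of 0.61–0.67, samples of 55 and 7 give a value rounding to 0.52 or less in 9–22% of draws. This also stands, but it weakens the null claim further. It is a matter of precision, whereas mixing the routes would persist at any sample size.
3. For discrimination among women who met this entry rule, truncation defines the population and is not a bias. True, and the result is labelled as group 2. But the stated aim is wider, the conclusion carries no such limit, and the pooling problem remains inside group 2.
4. The contrast with 0.78 concerns the same group and outcome. Also true. Post-operation length has no stated entry ceiling, but nothing in the documents shows how much of the gap is due to selection, so no claim about the gap's size is warranted.

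**Conclusion.** The concern holds as a limit on interpretation, not as a demonstrated bias. Selection on length, the history-dependent ceiling and the pooling are all explicit in the documents. The AUC of 0.52 is conditional on that selection. It may be attenuated relative to women with cervical insufficiency in general, and may be distorted in either direction by pooling. The distortion cannot be sized without the route split and the effect of history at equal length; the illustrative pooled range of 0.47–0.75 rests wholly on assumed inputs. It is also assumed that the pre-operation length in the ROC is the qualifying measurement or close to it, which the documents do not state. Even without the selection issue, an interval of about 0.29–0.75 does not establish absence of predictive value. Confidence that the negative conclusion is unsupported is high; confidence in the direction of any bias is low to moderate.

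**What to change.** - Report, for each group 2 entry route, the number of women, the number of failures and the distribution of pre-operation length.
- Give the pooled AUC with its 95% CI. Beside it, as a descriptive check, give a route-stratified AUC that counts only success–failure pairs from the same route, also with a 95% CI. Do this for both pre- and post-operation length, and state the number of failures behind each.
- Replace the conclusion with: predictive value of pre-operation length could not be determined in women selected on length by history-specific limits.

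The cost is a short reanalysis: history of premature birth and pre-cerclage length are both listed among the data collected. The drawback is imprecision. With about 7 failures, perhaps only 1–5 of them in the no-history route, estimates by route will be very wide and may not be interpretable. The table by route and the corrected sentence remain worthwhile even then.
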